8.7.2.5 Sensitivity Analysis

8.7.2.5.1 Subgroup Analysis

Subgroups of interest, including but not limited to those defined by characteristics listed below, may be explored, if sufficient numbers are available (eg, $n \ge 10$).

Table 2. List of Study Covariates for Subgroup Analyses

Covariate	Characteristics
Sex:	MaleFemale
Calendar year of sotorasib initiation	Before January 1, 2023On/after January 1, 2023
Brain metastasis at sotorasib initiation	YesNo
ECOG score at sotorasib initiation	 0 1 2 ≥ 3 Not available

Protocol Number: 20240175

Date: 27 March 2025 Page 32 of 47

Number of prior lines of therapy	• 1
	• 2
	≥ 3
Treated with PD-1/PD-L1 inhibitors prior to	• Yes
sotorasib initiation	• No
Adult patients with other cancer other than	• Yes
NSCLC	• No

[figure not shown]
8.7.2.5.2 Stratified Analysis

Not applicable

8.7.2.5.3 Sensitivity Analysis for Residual Confounding and Bias

In the absence of verified death information in BOAO Pilot Zone, such as data from death registries, the reported deaths are utilized for analysis. This may introduce a potential for underestimating survival rates. A sensitivity analysis will be conducted by excluding individuals who were lost to follow-up defined as those whose last activity is earlier than the data cutoff. The characteristics of patients with censoring will be outlined alongside those of patients without censoring, providing insights into their respective profiles.

We will also conduct a sensitivity analysis wherein patients with other actionable mutations (eg, ALK, EGFR) who have received treatment with targeted therapies other than sotorasib will be excluded, as the prognosis among such patient populations could be meaningfully different compared to patients not receiving these targeted therapies.

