8.2.1 Study Period

The study eligibility period extends from the patients' index date (ie, the initiation of sotorasib) to the end of study period, defined as the earliest occurrence of patient's last activity date in the data source, data cut-off date or death.

The first available sotorasib use in BOAO Pilot Zone is around August 2021 through a pre-registration program. Specifically, sotorasib was included in the following hospitals'

Protocol Number: 20240175

Date: 27 March 2025 **Page 20 of 47**

drug lists and available for prescription: Ruijin Hainan Hospital in July 2022; BOAO Super Hospital in August 2021; BOAO Hengda Hospital in November 2021; and BOAO future Hospital in January 2022. The data cut-off will be the EC submission date (~ Q2 2025).

Sotorasib was approved in Hong Kong on April 29, 2022. The eligible treatment should occur after April 29, 2022. The data cut-off will be the date of data extraction (~ Q3 2025).

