8.2.6 Study Follow-up

As the Hong Kong SAR CDARS database is a closed-loop database with linkage to the regional deaths registry, patients without evidence of death in the CDARS database by the data cut-off date were considered alive, and their last activity date will be the same as the cut-off date.

For the objective of OS, follow-up per patient will continue through earliest date of last clinical activity in the data source, data cut-off in the data source, or death.

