8.3.2 Outcome Assessment

Safety Outcomes

In BOAO Pilot Zone, the AEs recorded in the electronic health record database throughout the study period will be documented and analyzed. Detailed information in medical records including vital signs, concomitant treatments, results of routine laboratory testing, ECG, and radiology will be reviewed to verify these AEs. Severity grade of AEs will be further verified by investigators according to the Common Terminology Criteria for Adverse Events (CTCAE), version 5.0 (CTCAE v5.0).

The patient incidence of AE after sotorasib initiation, including:

- TEAE
- Adverse event of interest, inclusive of hepatotoxicity, interstitial lung disease/pneumonitis, and renal toxicity
- Treatment-related AEs
- Treatment-related AEs of grade 3 or worse
- Serious treatment-related AEs
- Treatment-related AEs leading to treatment discontinuation
- Treatment-related AEs leading to dose reduction
- Treatment-related AEs leading to death

[figure not shown]
In Hong Kong SAR CDARS database, only adverse event of interest, inclusive of hepatotoxicity, interstitial lung disease/pneumonitis, and renal toxicity will be documented and analyzed. Each event of interest is a grouping of individual preferred terms determined using the following standardized MedDRA queries (SMQs): drug-related hepatic disorders – comprehensive search (SMQ narrow) for hepatotoxicity; interstitial lung disease (SMQ narrow) for ILD/pneumonitis; and acute renal failure (SMQ narrow) for renal toxicity. Medical records including diagnosis, vital signs, concomitant treatments, results of routine laboratory testing, ECG, and radiology will be reviewed to identify and verify AE. Detailed testing and exams to review will be further clarified in the statistical analysis plan and eCRF.

Protocol Number: 20240175

Date: 27 March 2025 Page 23 of 47

OS

• OS: The time from the index date to death from any cause. Patients without evidence of death at data cutoff will be right-censored at their last activity date.

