8.4 Data Sources

In BOAO Pilot Zone, patients, often residing from across mainland China, need to be physically admitted to one of the several hospitals in BOAO Pilot Zone to receive sotorasib. The first hospitalization includes a complete medical history, radiology scans, tumor biomarker assessment, and liver and renal function tests to inform clinicians' decision to treat. As sotorasib is in the pre-registration program, the government requires close monitoring and reporting of safety events, which are well documented in the established hospital system. Hence, expectation that safety endpoints will be measured adequately in this study. As sotorasib is an oral medication taken daily until disease progression or unacceptable toxicity, patients need to physically return to the BOAO Pilot Zone hospital at least once per month initially, and every 3 months thereafter based on physician's assessment and justification, to continue therapy. Patients seeking refills require recent radiology results, organ function evaluation etc. reassessment. Refills can be initiated with online evaluations and subsequently processed through outpatient clinics at hospitals in Hainan. Reports from Tier A hospitals across China are accepted. A case report form created for this study will be used to extract the relevant structured and unstructured data from the electronic heath record.

In Hong Kong SAR, this study will be using the electronic health records of the CDARS database managed by the Hong Kong Hospital Authority, a statutory body in charge of all public hospitals and their ambulatory clinics in Hong Kong SAR. Anonymized patient data are transferred daily to CDARS for audit purposes from the clinical management system (CMS) of the Hospital Authority, which contains medical records including: demographic information, diagnoses, prescription records, laboratory tests, accident and emergency attendance, outpatient clinics, hospital stay, and discharge information of patients since 1993. It also contains data on causes of death through its internal linkage

Protocol Number: 20240175

Date: 27 March 2025 Page 26 of 47

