8.9 Limitations of the Research Methods

8.9.1.1 Measurement Errors

As no verified death information is linked (eg, death registry) in BOAO Pilot Zone, the reported death is used. Because of this, it is likely the survival is underestimated. Sensitivity analysis excluding those lost to follow up will be performed.

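### Excluding BOAO patients whose last activity precedes the cut-off removes censored patients but keeps deaths, so this OS sensitivity analysis is biased downward even when loss is non-informative.

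*Protocol*

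**What the plan says.** Section 8.7.2.5.3 plans a BOAO sensitivity analysis "excluding individuals who were lost to follow-up defined as those whose last activity is earlier than the data cutoff". Section 8.9.1.1 gives the reason, "As no verified death information is linked (eg, death registry) in BOAO Pilot Zone, the reported death is used", says that survival is therefore likely to be underestimated, and repeats the plan without narrowing the definition: "Sensitivity analysis excluding those lost to follow up will be performed".

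Other sections determine how the rule acts:

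- Main OS analysis (Section 8.3.2): "Patients without evidence of death at data cutoff will be right-censored at their last activity date".
- End of OS follow-up (Section 8.2.6): "follow-up per patient will continue through earliest date of last clinical activity in the data source, data cut-off in the data source, or death".
- BOAO cut-off (Section 8.2.1): the ethics committee submission date, about Q2 2025. This is one administrative date, not tied to visits.
- BOAO contacts on therapy (Section 8.4): "at least once per month initially, and every 3 months thereafter".
- Hong Kong (Section 8.2.6): patients not known dead have their last activity set to the cut-off, so the rule removes no living patient there. Section 8.7.2.1 analyses the regions separately, so Hong Kong cannot dilute the effect in BOAO.
- Section 8.9.3 plans another sensitivity analysis, which follows patients without evidence of death to the end of the study.

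**The concern.** There are two separate faults.

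First, the definition does not distinguish a lost patient from one between visits. With contacts up to 3 months apart and a single cut-off day, a living BOAO patient under regular follow-up will nearly always have a last recorded activity before that day.

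Second, even with a good definition, exclusion is the wrong operation. Whether a patient is later lost is not known at the index date. Removing such patients discards event-free person-time and keeps every reported death. The result moves downward whether or not loss is related to prognosis.

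At stake is the reading of the secondary endpoint. A clear drop in this analysis would suggest that OS in BOAO is fragile, when the drop is produced by the method. The stated rationale also has the wrong direction: a death that is not reported leaves the patient censored, which raises the survival estimate.

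**Working it through.** The plan gives no figure for this analysis. Its only precision figure reproduces, 1.96 × √(0.5 × 0.5 / 115) = 9.14%, but has no bearing here.

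**Direction (no simulation needed).** At each death time the Kaplan-Meier factor is 1 − d/n. Removing c censored patients who were at risk gives 1 − d/(n − c), which is never larger. For the first death among 100 patients of whom 32 are later removed, the factor goes from 1 − 1/100 = 0.990 to 1 − 1/68 = 0.985. The curve can only fall or stay equal.

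**Inputs.** About 100 BOAO patients (Section 8.5). First use in August 2021 and cut-off about Q2 2025 (Section 8.2.1), taken as 45 months. Reference median OS of 10.6 months, 95% CI 8.9 to 14.0, and median PFS of 5.6 months from the phase III trial (Section 4). Assumed, not in the protocol: uniform entry, visits monthly to month 3 and then 3-monthly, deaths dated exactly, and one of two OS shapes:

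- A: exponential OS, median 10.6 months.
- B: exponential treatment time (median 5.6 months, PFS as proxy) plus an exponential post-treatment time set so that the OS median is 10.6 months.

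**Reading 1: activity counted only up to the cut-off, deaths kept.** For shape A, λ = ln 2 / 10.6 = 0.0654 and A = 45. The expected proportion dead is 1 − (1 − e^(−λA))/(λA) = 1 − 0.947/2.943 = 0.678. Survival time among decedents has density proportional to λe^(−λt)(45 − t); its median is 6.95 months. Simulation with n = 100 and no true loss agrees: about 68 deaths, 31.6 living patients excluded and 0.5 kept.

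| Shape | True median, 12-month OS | After exclusion |
|---|---|---|
| A | 10.6 months, 45.6% | 7.0 months, 29% |
| B | 10.6 months, 43.5% | 8.7 months, about 33% |

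Under shape A the main analysis, censoring at last visit, gives 10.2 months and 44%. Varying shape A, the median after exclusion is 6.3, 7.7 and 8.1 months for true medians of 8.9, 12.5 and 14.0 months, and 6.3 months for 36 months' entry with a true median of 10.6.

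**Reading 2: later chart entries count, so only truly lost patients are dropped.** With random loss of 0.02 per month, about 17% are lost. Excluding them gives 8.8 months (A) or 9.6 months (B). Keeping the same patients and censoring them at loss returns 10.6 months. At 1% or 3% loss per month, shape A gives 9.7 or 8.1 months after exclusion.

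**Effect of a window alone.** Under shape A with a 3-month tolerance and no true loss, nobody living is dropped and the median stays at 10.3 months, equal to the main analysis. With 3% loss per month, about 23 patients are dropped and the median falls from 9.9 to 7.9 months. A window cures the definition but not the exclusion.

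**Unreported deaths.** Under shape A with 20% of deaths unreported and those patients censored at last activity, the main analysis gives 12.6 months against a truth of 10.6. The bias is upward. After the planned exclusion the median is 6.9 months, almost the same as the 7.0 months with every death reported. The analysis does not register the problem it is meant to test.

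**The case against.** A reader might infer that the rule certainly leaves only decedents. The documents do not settle this. Section 8.2.6 lists last activity and cut-off separately, and the cut-off is the submission date for an ethics review that has still to take place (Section 9.2), so charts may hold later entries at extraction. Section 6.3 also describes physicians documenting follow-up inside and outside BOAO, and Section 8.4 allows refills to start online, so contacts may be denser than the visit grid. This stands: it limits the larger shift to Reading 1. It does not rescue the analysis, because Reading 2 is still biased downward.

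A reader might also infer that nobody is left, since a decedent's last activity precedes the cut-off too. The next sentence of Section 8.7.2.5.3 contrasts patients with and without censoring, so the rule is aimed at censored patients and reported deaths stay.

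Nor is this shown to be the main check on OS. Section 8.9.3 has an analysis that errs the other way, and Section 8.7.2.5.3 also compares the characteristics of censored and uncensored patients. It can fairly be said that the excluded-set median lies below the truth in every scenario above, so it acts as a crude low value. But it is not constructed as a bound: if unreported deaths are mostly early ones, the exclusion removes those early deaths as well.

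Finally, the study is descriptive, safety is primary, and the main OS analysis keeps every patient. That argues for a lower severity, not for leaving the rule as it is.

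**Conclusion.** The point holds. The protocol fixes a rule that gives a misleading result; this is not detail left to the analysis plan. The direction follows from the Kaplan-Meier formula under either reading.

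The size rests on assumptions. For a true median of 10.6 months and 45 months' uniform entry, the median falls to about 7.0 to 8.7 months and 12-month OS to about 29% to 33% (truth 44% to 46%) if nearly only decedents remain. The median falls to about 8.8 to 9.6 months if a random 17% are lost and only they are excluded. The ranges reflect the two assumed OS shapes.

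The analysis therefore cannot show whether OS is sensitive to loss to follow-up or to unreported deaths, and Sections 8.7.2.5.3 and 8.9.1.1 give the wrong direction for the latter. Censoring at last visit does pull the median down slightly (10.2 months against 10.5 with complete follow-up, shape A), but that comes from how censoring is dated, not from missing deaths.

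Severity: should-fix. OS is secondary and the main analysis in Section 8.3.2 is unaffected.

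**What to change.** In Sections 8.7.2.5.3 and 8.9.1.1, replace the exclusion analysis with the following:

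1. Define a BOAO patient as lost to follow-up if not known to be dead and without a recorded contact within a window before the cut-off that is longer than the 3-month visit interval, for example 120 days. State whether chart entries after the cut-off count.
2. Keep every patient at risk until last contact, and report the number and percentage lost.
3. As an explicitly labelled pessimistic bound, count the lost patients as dead shortly after last contact, for example 30 days later.
4. Present it beside the Section 8.9.3 analysis that follows patients to the end of the study, labelled as the optimistic bound.
5. Correct the stated direction: unreported deaths censored at last activity make OS look longer.

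The 120 and 30 days are proposals for the team to settle. The pessimistic analysis also shifts OS by construction (about 8.5 to 9.0 months under the same random 17% loss), so it must be read only as a bound and not as evidence that loss is informative. Unreported deaths inside the window would still be censored.

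The cost is protocol and analysis plan wording and one program, with no new data. The downside is that the pessimistic bound may look less favourable.

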8.2 Setting and Study Population

Two regions will be included in the study, ie, BOAO Pilot Zone and Hong Kong SAR.

Until data cut-off date, approximately 100 sotorasib treated patients in Hainan BOAO Pilot Zone, and about 15 patients in Hong Kong SAR, will be eligible for medical chart review. Details of data sources are provided in Section 8.4.

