8.7.2 Planned Method of Analysis

8.7.2.1 General Considerations

All data analyses will be performed using appropriate software such as SAS statistics software version 9.3 or higher (SAS Institute Inc., Cary, NC). An analysis plan with a detailed description of analyses to be performed will be developed.

All analysis will be conducted separately for patients in BOAO Pilot Zone and Hong Kong SAR CDARS.

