8.9.3 Analysis Limitations

CCI
We will perform a sensitivity analysis in which patients who
switch to other commercially available drugs or clinical trial medications will be censored
for sotorasib treatment.
Estimates of OS are likely to be immature in this study due to the potentially short
observation period for some patients. Patients without evidence of death by the data
cut-off will be censored at their last confirmed activity date, potentially underestimating
the true time at risk. A sensitivity analysis will follow these patients to the end of the
study instead of censoring them at their last confirmed activity date.
CCI

Protocol Number: 20240175

Date: 27 March 2025 Page 35 of 47

No further analysis limitations are expected.

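### Section 8.7.2.5.3 compares BOAO patients with and without censoring, which under the OS rule means patients without a reported death against reported deaths, so the table cannot tell informative from uninformative loss to follow-up

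*Protocol*

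**What the plan says.** Protocol 8.7.2.5.3 opens with the weakness it addresses: "In the absence of verified death information in BOAO Pilot Zone, such as data from death registries, the reported deaths are utilized for analysis". It then plans an OS analysis that leaves out patients "lost to follow-up defined as those whose last activity is earlier than the data cutoff". The next sentence changes term, from loss to censoring: "The characteristics of patients with censoring will be outlined alongside those of patients without censoring, providing insights into their respective profiles".

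Censoring is defined in 8.3.2: "Patients without evidence of death at data cutoff will be right-censored at their last activity date". Section 8.9.3 repeats the rule, saying that patients with no evidence of death by the "cut-off will be censored at their last confirmed activity date", and warns: "Estimates of OS are likely to be immature in this study due to the potentially short" observation period of some patients.

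BOAO supplies most of the data ("approximately 100 sotorasib treated patients in Hainan BOAO Pilot Zone", against about 15 in Hong Kong) and is analysed on its own: "All analysis will be conducted separately for patients in BOAO Pilot Zone and Hong Kong SAR CDARS". Section 8.2.1 puts first use in BOAO at about August 2021 and the cut-off at about Q2 2025, with no minimum follow-up.

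**The concern.** Without a death registry in BOAO, the Kaplan-Meier OS curve relies on loss to follow-up being unrelated to prognosis. A description of who is censored should help a reader judge that. As its groups are fixed, the planned one splits patients by the outcome itself.

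Two consequences follow. Performance status, brain metastases, prior lines and year of initiation will differ between the columns simply because they predict death or length of follow-up. And if sicker patients are the ones who drop out, they move into the censored column and pull its profile towards that of the deaths. The table may then look more balanced in the situation that matters most. At stake is how BOAO OS is interpreted.

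**Working it through.** **Plan's own figure.** The only design figure is the margin of error in 8.5: √(0.5 × 0.5 × 1.96² / 115) = 9.14%, which reproduces. For BOAO alone, n = 100, it is 9.80%. The point does not rest on it.

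**Who is in each column.** By 8.3.2:
- Without censoring: reported deaths only.
- With censoring: alive and followed to cut-off, lost earlier, or dead but unreported.

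Nothing in 8.7.2.5.3 separates these three.

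**Inputs for the size.**
- From the protocol: entry August 2021 to about Q2 2025, taken as A = 45 months; median OS 10.6 months (the phase III figure in the Abstract).
- Assumed, because the protocol gives no values: uniform entry, exponential survival, a poor-prognosis factor with prevalence 20-40% and death hazard ratio (HR) 1.5-3, and the loss rates below.

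**Formulas.** For a prognosis group with death hazard λ and loss hazard μ per month, let h = λ + μ.
- Followed alive to cut-off: a = (1 − e^(−hA)) / (hA)
- Died: (λ/h)(1 − a)
- Lost: (μ/h)(1 − a)

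**No loss, prevalence 30%, HR 2.**
1. Set the overall median to 10.6 months: 0.7x + 0.3x² = 0.5 with x = e^(−10.6λ). This gives x = 0.5734, so λ = 0.0525 (good prognosis) and 0.1049 (poor).
2. Censored fraction, good prognosis: (1 − e^(−2.361))/2.361 = 0.3836. Poor: (1 − e^(−4.722))/4.722 = 0.2099.
3. All censored: 0.7 × 0.3836 + 0.3 × 0.2099 = 0.3315.
4. Factor among censored: 0.0630/0.3315 = 19.0%. Among deaths: 0.3 × 0.7901/0.6685 = 35.5%. The gap is −16.5 points with nobody lost.

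Over prevalence 20-40% and HR 1.5-3, the no-loss gap runs from about −8 to −29 points. Calendar time separates the columns too: in simulation, mean entry month is 31.6 for censored patients and 17.9 for deaths.

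**With loss, prevalence 30%, HR 2** (gaps from unrounded values):

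| Loss per month, good / poor prognosis | Lost | Factor in censored | Factor in deaths | Gap (points) |
|---|---|---|---|---|
| none | 0% | 19.0% | 35.5% | −16.5 |
| 3% / 3% (unrelated) | 24% | 22.0% | 37.3% | −15.2 |
| 2% / 4% | 21% | 25.3% | 34.0% | −8.7 |
| 2% / 6% | 23% | 28.2% | 31.6% | −3.4 |
| 2% / 8% | 25% | 30.5% | 29.5% | +1.0 |
| 1.5% / 6% | 20% | 29.2% | 30.7% | −1.4 |

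Unrelated loss looks almost the same as no loss. As loss becomes more informative, the columns converge.

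**The gap does not identify the mechanism.** At prevalence 30%, a gap of about −10 points arises with no loss at HR 1.5 (23.2% vs 33.3%). It also arises with fourfold informative loss (1.5% / 6%) at HR 3 (24.5% vs 34.8%).

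**What does identify it.** Expected losses in a group equal μ times its person-time at risk, so the ratio of loss rates recovers the ratio of the μ values. Simulated cohorts of 100 gave 1.01, 2.00, 2.97 and 3.98 for true ratios 1, 2, 3 and 4. A plain lost versus not-lost table does not do this: with unrelated loss of 3% per month it shows about 23% vs 32%, because patients who die early have less time to be lost.

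**The case against.** **Another reading.** The sentence directly follows the definition of loss, so patients with censoring could mean those just excluded. The text does not say so, and 8.3.2 and 8.9.3 define censoring otherwise. Nor would that reading rescue the table: last activity before cut-off, taken literally, also catches patients who died and living patients between visits, which 8.4 puts up to 3 months apart.

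**Left to the analysis plan.** Table layout usually is. Here, however, the protocol itself names the two groups.

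**Only descriptive.** This stands. No test, threshold or inference is attached. A reader might infer that the report would reach the opposite conclusion about the validity of OS. The documents do not support that, since they attach no conclusion to the table. They also disclose incomplete deaths (8.9.1.1, 8.9.4) and plan two other OS sensitivity analyses: excluding lost patients, and following patients without evidence of death to study end (8.9.3).

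**Masking is not certain.** This also stands. A reader might infer that the table always hides informative loss. With loss of 1.5% / 6% per month, HR 3 leaves 24.5% vs 34.8%, and HR 1.5 reverses it to 32.7% vs 27.7%. A reversal would itself be a visible warning. Masking is a tendency that depends on assumed values.

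**Sampling error.** With 100 patients the gap has a standard deviation of about 9 points. The 95% range is about −34 to +1 with no loss and −19 to +17 at 1.5% / 6% (HR 2). One table would seldom support a confident reading either way, which is a further reason not to rely on it.

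**Conclusion.** The point holds as a badly fixed comparison. From the protocol's definitions alone, the two columns are patients without a reported death and reported deaths, with censoring at cut-off and loss mixed in the first. The table therefore cannot separate informative from uninformative loss.

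The size rests on assumptions. The built-in gap of about 8 to 29 points depends on the assumed prevalence, HR, uniform entry and exponential survival. The shrinking or reversal depends also on the assumed loss rates. Loss of healthier patients was not modelled; it would be expected to add to the gap already present without loss, so it could not be recognised either.

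The consequence is limited to interpreting BOAO OS, a secondary endpoint. The primary safety analysis is untouched, and nothing here shows that the OS estimate is itself wrong. The change is worth making because it is nearly free.

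**What to change.** Replace the sentence in 8.7.2.5.3 with wording such as: *Characteristics of BOAO patients will be described in three groups: died; alive and under follow-up at data cut-off, allowing for the scheduled visit interval; and lost before cut-off without a reported death. Loss will be described by baseline characteristic (ECOG, brain metastasis, prior lines, year of initiation), one at a time, as a rate per person-time or by reverse Kaplan-Meier, with time at risk ending at death or data cut-off.*

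The visit window should be stated and taken from the intervals in 8.4. The rate or time-to-loss form is needed because simple proportions among lost patients are distorted by early deaths.

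Cost: one sentence and one extra table, from data already being extracted. The lost group may be small, roughly 10-25 patients under the assumed loss rates, so the description will be imprecise and a multivariable Cox model should not be required. Unreported deaths will still sit in the lost group; without a registry, no table can separate them.
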